4.6.3 Clinical Laboratory, Blood Sample

4.6.3.1 Definitions and Derivations

Blood samples for the determination of clinical chemistry and haematology will be taken at the visits indicated in the CSP.

The rules described in Sections [3.3.1](#), [3.3.4](#), [3.3.5](#), and [3.3.6](#) of this document considering the definition of baseline, visit windows, handling of multiple records and records above or below the limit of quantification are followed.

Absolute values are compared to the reference range and classified as low (below range), normal (within range or limits of range), and high (above range). Local reference ranges are used for the primary interpretation of laboratory data.

Changes from baseline in clinical chemistry and haematology will be calculated for each post-dose visit, including the safety follow-up visit for participants who are off treatment.

All laboratory results will be converted to standard units, and CTCAE grades (version 5.0) will be derived at each visit according to the CTCAE grade criteria. For parameters where CTCAE grades are defined and some parameters may have both high- and low-range values, CTCAE grades will be calculated for each set of high and low values. Laboratory parameters that will be summarised, along with details of whether the maximum and/or minimum are of interest and the availability of CTCAE grading are given in [Table 17](#).

Table 17 **Haematology and clinical chemistry parameters - Minimum/Maximum of interest**

Laboratory Assessment	Maximum of interest	Minimum of interest	CTCAE grading available
Albumin		Yes	Yes
Alkaline phosphatase	Yes		Yes
Alanine aminotransferase	Yes		Yes
Aspartate aminotransferase	Yes		Yes
Total calcium	Yes	Yes	No
Creatinine	Yes		Yes
Gamma-glutamyl transferase	Yes		Yes
Magnesium	Yes	Yes	Yes
Phosphate	Yes	Yes	No
Potassium	Yes	Yes	Yes
Sodium	Yes	Yes	Yes
Total Protein		Yes	No

Total bilirubin	Yes		Yes
Blood urea nitrogen	Yes		No
Creatine kinase	Yes		Yes
Amylase	Yes		Yes
Haemoglobin	Yes	Yes	Yes
Platelets		Yes	Yes
Leukocytes (absolute)	Yes	Yes	Yes
Neutrophils (absolute)		Yes	Yes
Lymphocytes (absolute)	Yes	Yes	Yes
Total red blood cell count		Yes	No

CTCAE, Common Terminology Criteria for Adverse Events.

For parameters with no CTCAE grading that are listed in the [Table 17](#), any on-treatment increase/decrease and TELC are derived. An on-treatment increase is defined as an increase to a value above the upper local laboratory reference limit at any time on treatment for participants with a value below the upper local laboratory reference limit at baseline. An on-treatment decrease is defined as a decrease to any value below the lower local laboratory reference range limit at any time on treatment for participants with a value above the lower local laboratory reference limit at baseline. A TELC is defined as any on-treatment increase or decrease from baseline.

4.6.3.2 Presentations

Haematology and clinical chemistry data will be summarised by scheduled visit using descriptive statistics over time in terms of absolute values and changes from baseline.

Shift tables showing CTCAE grade changes from baseline to worst CTCAE grade on treatment will be produced for parameters with available CTCAE grades (see [Table 17](#)). For specific parameters, separate shift tables indicating the hyper- and hypo-directionality of change are produced (see [Table 17](#) parameters with “Yes” for maximum of interest, “Yes” for minimum of interest, and “Yes” for CTCAE grading available). Percentages are based on the number of participants with a baseline value and an on-treatment value.

For parameters in [Table 17](#) with no CTCAE grading (“No” for CTCAE grading available), the number and percentage of participants with any on-treatment increase from baseline, any on treatment decrease from baseline, and a TELC are summarised. Percentages for an increase from baseline are based on the number of participants with a baseline value below

the upper local laboratory reference limit and an on-treatment value. Percentages for a decrease from baseline are based on the number of participants with a baseline value above the lower local laboratory reference limit and an on-treatment value. Percentages for a TELC are based on the number of participants with a baseline value and an on-treatment value.

Haematology and clinical chemistry data in [Table 17](#) will also be presented graphically using boxplots for absolute values and changes from baseline by scheduled visit.

A listing will be provided for participants with potential Hy's law (ALT or AST $\geq 3 \times$ the ULN and total bilirubin $\geq 2 \times$ ULN), where the onset date of ALT or AST elevation is prior to or on the date of total bilirubin elevation.

Laboratory data for the variables displayed in the CSP Table 13 will be listed. Site reference ranges will also be listed. Flags (H or L) will be applied to values falling outside reference ranges (which will be explicitly noted on these listings where applicable) and for the CTCAE grade for parameters for which CTCAE grading applies.

Pregnancy data will also be listed.

4.6.4 Clinical Laboratory, Urinalysis

4.6.4.1 Definitions and Derivations

Urine samples for the determination of urinalysis are collected as described in the CSP.

The rules described in Sections [3.3.1](#), [3.3.4](#), [3.3.5](#), and [3.3.6](#) of this document considering the definition of baseline, visit windows, how to handle multiple records and records above or below the limit of quantification are followed.

4.6.4.2 Presentations

Urinalysis data will only be listed, and no summary tables will be produced. Site reference ranges will also be listed. Flags (H or L) will be applied to values falling outside reference ranges (which will be explicitly noted on these listings where applicable) and to values for which CTCAE grading applies.

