# **3 OBJECTIVES AND ENDPOINTS**

The objectives and endpoints of the study are shown in Table 5.

Objectives	Endpoints		
Primary			
• To determine the PK of selumetinib after administration of the selumetinib granule formulation.	• Selumetinib AUC0-12 derived after single dose administration.		
• To assess the safety and tolerability of the selumetinib granule formulation.	
 
Safety and tolerability will be evaluated in terms of AEs, clinical safety laboratory assessments (clinical chemistry, haematology, urinalysis), physical examination, weight, vital signs, ECG, ECHO, ophthalmologic assessment, knee (or wrist) MRI/X-ray, and performance status.
 
Assessments related to AEs will include: occurrence/frequency; relationship to study intervention; CTCAE grade; seriousness; death; AEs leading to discontinuation of study intervention; AEs of special interest.
 
		
Secondary			
• To assess the palatability of the selumetinib granule formulation	• Palatability will be assessed using the parent-reported observer palatability assessment.		
To further assess the PK of selumetinib and N-desmethyl selumetinib metabolite after administration of the selumetinib granule formulation.	
 
Plasma concentrations and PK parameters of selumetinib including, but not limited to:         
 
Selumetinib AUC0-12 derived after multiple dose administration.
 
Cmax, AUC0-6, AUClast, CL/F, tmax, tlast derived after single and multiple dose administration.
 
AUC0-24, Vz/F and t½λz after single dose administration.
 
AUC0-24, Vz/F and t½λz after single dose administration.
 
Rac Cmax, Rac AUC0-12, and Vss/F derived after multiple dose administration.
 
 
 
Plasma concentrations and PK parameters of N-desmethyl selumetinib including, but not limited to:         
 
Cmax, AUC0-6, AUC0-12, AUClast, tmax, tlast derived after single and multiple dose administration.
 
Rac Cmax and Rac AUC0-12 derived after multiple dose administration.
 
 
 
Parent-to-metabolite ratio for AUC0-6, AUC0-6, AUC0-12 and AUC0-24 (single dose only), and Cmax after single and multiple dose administration.
 
		
• To evaluate the efficacy of the selumetinib granule formulation by assessment of ORR as determined by ICR per REiNS criteria.	Objective Response Rate		
Endpoints			
--			
CCI     CCI     CCI     CCI     CCI      CCI			
Parent-reported CCI     total score.			
• CCI			

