## 8.3.9 Clinical Safety Laboratory Assessments

Blood and urine samples for determination of clinical chemistry, haematology and urinalysis will be taken at the visits indicated in the SoA.

Additional safety samples may be collected if clinically indicated at the discretion of the Investigator. The date, time of collection, and results (values, units and reference ranges) will be recorded on the appropriate eCRF.

The clinical chemistry, haematology and urinalysis will be performed at a local laboratory at or near to the investigator site. Sample tubes and sample sizes may vary depending on laboratory method used and routine practice at the site.

The laboratory variables shown in Table 13 will be measured.

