#### Clinical Study Protocol -5.0 Selumetinib - D1346C00004 **Table 13** Laboratory Safety Variables

Haematology/Haemostasis (whole blood)	Clinical chemistry (serum or plasma)
B – Haemoglobin	S/P – Albumin
B – Platelet count	S/P – Alkaline phosphatase
B – Leukocyte count	S/P – Alanine aminotransferase
B – Leukocyte differential count (absolute count)	S/P – Aspartate aminotransferase
B – Absolute Neutrophil count	S/P – Total calcium
B – Absolute Lymphocyte count	S/P – Creatinine a
B – Total white blood cell count	S/P – Gamma-glutamyl transferase
B – Total red blood cell count	S/P – Magnesium
	S/P – Phosphate
	S/P – Potassium
	S/P – Sodium
Urinalysis (dipstick) b	S/P – Total protein
U – Glucose	S/P – Total bilirubin
U – Protein/albumin	S/P – Urea nitrogen c
U – Haemoglobin/erythrocytes/blood	S/P – Creatine kinase d
	S/P – Amylase
	S/P – Troponin (isoform per site norm) e

a. Creatinine clearance and glomerular filtration rate to be calculated at screening and if clinically indicated.

b. Urine microscopy will be assessed if other urinalysis measurements are abnormal or if clinically indicated

c. Urea or blood urea nitrogen based on local site practice.

d. Creatine Kinase to be assessed in accordance with the schedule of assessments and if unexplained muscle weakness or myalgia (muscle pain) occurs. See Section 8.3.1 for additional information.

e. Troponin (isoform per site norm), should be assessed at screening, and performed when there is a significant drop in LVEF (of ≥10 percentage points relative to baseline and to an absolute LVEF below the institution's LLN on study intervention) or for any cardiorespiratory events with no obvious diagnosis. If troponin assessments are not available, per local practice, CK-MB isoform should be assessed. Participants should be managed according to the algorithm provided in Appendix E 2.

B, blood; CK-MB, creatine kinase-myocardial band; LLN, lower limit of detection; LVEF, left ventricular ejection fraction; P, plasma; S, serum; U, urine.

In case a participant shows an AST or  $ALT \ge 3 \times ULN$  together with total bilirubin  $\ge 2 \times ULN$  please refer to Appendix D, Actions required in cases of increases in liver biochemistry and evaluation of Hy's Law, for further instructions.

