#### 8.4.5 Adverse Events Based on Examinations and Tests

The results from the CSP mandated laboratory tests, vital signs, physical examinations, ECGs, ECHO scans and ophthalmological examinations will be summarised in the Clinical Study Report.

Deterioration as compared to baseline in CSP-mandated laboratory tests, vital signs, ECGs, echocardiogram scans and ophthalmological examinations should therefore only be reported as AEs if they fulfil any of the SAE criteria, are the reason for discontinuation of treatment with the investigational product or are considered to be clinically relevant as judged by the Investigator (which may include but not limited to consideration as to whether treatment or non-planned visits were required or other action was taken with the study intervention, eg, dose adjustment or drug interruption).

If deterioration in a laboratory value/vital sign/ECG/ECHO is associated with clinical signs and symptoms, the sign or symptom will be reported as an AE and the associated laboratory result/vital sign/ECG/ECHO will be considered as additional information. Wherever possible the reporting Investigator uses the clinical, rather than the laboratory term (eg, anaemia versus low haemoglobin value). In the absence of clinical signs or symptoms, clinically relevant deteriorations in non-mandated parameters should be reported as AE(s).

Deterioration of a laboratory value, which is unequivocally due to disease progression, should not be reported as an AE/SAE.

Any new or aggravated clinically relevant abnormal medical finding at a physical examination as compared with the baseline assessment will be reported as an AE unless unequivocally related to the disease under study.

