3.3.1 Baseline and Change from Baseline Definition

Baseline is defined as the last non-missing value obtained prior to the first dose of selumetinib.

Assessments on the day of the first dose where time is not captured will be considered prior to the first dose if such procedures are required by the CSP to be conducted before the first dose.

If two or more measures are recorded on the same day with no time (or on the same day with the same time/timepoint), then the average will be used as the baseline. For nonnumeric laboratory tests (ie, some of the urinalysis parameters) where taking an average is not possible, then the best value would be taken as baseline as this is the most conservative.

In all summaries, the change from baseline variables will be calculated as the posttreatment value -minus the value at baseline.

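### Urinalysis is a named part of the primary safety endpoint but is only listed, although the protocol limits AE reporting of laboratory changes because those results are to be summarised

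*SAP*

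**What the plan says.** **Endpoint.** Protocol Section 3 (Table 5) defines primary safety and tolerability through a list that includes "clinical safety laboratory assessments (clinical chemistry, haematology, urinalysis), physical examination, weight, vital signs". Protocol 8.3.9 makes urine testing a scheduled procedure: "Blood and urine samples for determination of clinical chemistry, haematology and urinalysis will be taken at the visits indicated in the SoA". Table 13 specifies a dipstick for glucose, protein/albumin and haemoglobin/erythrocytes/blood.

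**AE rule.** On what the study report will contain, protocol 8.4.5 opens with "The results from the CSP mandated laboratory tests, vital signs, physical examinations, ECGs, ECHO scans and ophthalmological examinations will be summarised". It continues that deteriorations in laboratory tests and several other assessments "should therefore only be reported as AEs if they fulfil any of the SAE criteria", cause discontinuation of treatment, or are clinically relevant in the investigator's judgement.

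**Protocol analysis section.** Protocol 9.4.3.1 promises summary statistics for laboratory assessments where appropriate, and frequency tables for categorical variables. It names haematology and clinical chemistry for change-from-baseline and grade-shift tables. For other safety assessments, such tables are optional.

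**SAP.** The primary safety row of the endpoint table in 4.2 includes laboratory assessments, with descriptive statistics as the summary. For urinalysis, 4.6.4.2 says "Urinalysis data will only be listed, and no summary tables will be produced". The listing carries flags for out-of-range and CTCAE-gradable values. Section 2, on changes to the protocol's planned analyses, is marked not applicable.

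**The concern.** The restriction in protocol 8.4.5 is a bargain. Routine laboratory changes need not be recorded as adverse events because the study report will summarise them anyway; the word *therefore* makes the summary the reason for the restriction. For haematology and chemistry the SAP keeps its side. For urinalysis it does not, so the AE route is narrowed on the strength of a summary that is not produced.

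What is at stake is a count. In a small single-arm study of children who, as protocol 2.3.3 notes, may be unable to report toxicity themselves, the number and percentage with a new abnormality is the natural output for an objective test. One named component of the primary safety endpoint would have no such figure.

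**Working it through.** The plan gives no figure to reproduce. The check follows a result through the documents and then counts how many results are affected.

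**Step 1: which outputs could contain a urinalysis result?**

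| Output | Source | Urinalysis included? |
|---|---|---|
| Visit summaries, change from baseline, boxplots | SAP 4.6.3.2 | No; haematology and chemistry only |
| CTCAE shift tables; treatment-emergent laboratory change tables | SAP 4.6.3.2, driven by Table 17 | No; Table 17 has no urine parameter |
| Urinalysis summary | SAP 4.6.4.2 | Ruled out |
| AE tables | SAP 4.6.2.2, fed by protocol 8.4.5 | Only if serious, a cause of discontinuation, or judged clinically relevant |
| Table of other significant AEs (OAEs) | SAP 4.6.2.1 and 4.6.2.2 | Only if the sponsor's expert review selects it |
| Listing with flags | SAP 4.6.4.2 | Yes |

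**Step 2: an example.** Take a child whose dipstick protein is negative at baseline and positive on treatment, with no serious event, no discontinuation and no finding of clinical relevance. Under protocol 8.4.5 this is not an AE. Unless the expert review makes it an OAE, it reaches only the last row of the table above.

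**Step 3: how many results are involved?** The urinalysis row of the schedule of activities (protocol Table 2) marks 16 time points: screening, C1D1, C1D15, Day 1 of C2, C3, C4, C5, C7, C9, C11, C13, C17, C21 and C25, end of treatment, and 30-day follow-up.

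- Screening and C1D1 supply the baseline and cannot be new or worse: 16 - 2 = 14 visits.
- 14 visits x 3 analytes = 42 post-baseline results per child.
- Of these, the 12 cycle visits give 12 x 3 = 36, end of treatment gives 3, and the 30-day follow-up gives 3.

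The 42 is a ceiling for Table 2. A child who stops early has fewer results. The long-term follow-up schedule (Table 3) and unscheduled samples would add to it.

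**Step 4: is a baseline rule available?** Yes. SAP 3.3.1 takes the last non-missing pre-dose value. For several same-day non-numeric results it adds: "where taking an average is not possible, then the best value would be taken as baseline". No planned urinalysis table uses this rule.

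**The case against.** The strongest reply is that protocol 9.4.3.1, not 8.4.5, governs the safety analysis. It qualifies laboratory summaries by appropriateness, requires change and shift tables only for haematology and chemistry, and leaves them optional elsewhere. Protocol 8.4.5 instructs investigators on recording and does not specify a table. This stands in part: a reader might infer that the SAP omits a shift table the protocol requires, and the documents do not support that. It does not remove the mismatch, because 8.4.5 still gives the summary as its reason for limiting AE reporting, and SAP 4.2 still assigns descriptive statistics.

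A reader might also infer that most laboratory changes, or important urinary signals, go unreported. The documents give no proportion. Clinically relevant dipstick changes still become AEs, including where treatment, an unplanned visit or dose action was needed. Abnormal dipsticks lead to urine microscopy (Table 13, footnote b), marked abnormalities may become tabulated OAEs, and the listing retains everything. Nor can urinalysis be set apart from physical examination: both are listing-only (SAP 4.6.12.2 for the latter) and both have a clinical-relevance route to AEs.

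Three further points on that side are fair:

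- The best-value rule in SAP 3.3.1 is a same-day tie-break, so it does not show that a table was intended.
- Protocol Table 4 lists no renal or urinary risk. Against that, protocol 8.3.1 calls for urine analysis in unexplained muscle weakness or myalgia, and the muscular-toxicity AESI terms include urinary myoglobin and acute kidney injury.
- Dipsticks are read at local laboratories and the plan defines no ordered categories, so a table needs a small new derivation.

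**Conclusion.** The point holds in limited form. A named component of the primary safety endpoint has no planned count, protocol 8.4.5 and SAP 4.2 both indicate that there should be a summary, and SAP Section 2 does not declare the departure. The gap covers new or worse dipstick results that are non-serious, do not cause discontinuation, are judged not clinically relevant and are not selected as OAEs. Investigator and expert judgement are useful safeguards but are not systematic counts.

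Up to 42 post-baseline results per child on the Table 2 schedule are shown only in a listing. That measures data volume, not harm: the documents give no rate of dipstick abnormality, so the number of uncounted findings cannot be estimated. The figure assumes that every scheduled visit takes place and that C1D1 is part of the baseline. No hypothesis test is affected, since safety is descriptive. The change is worth making because it is cheap and closes an inconsistency in the primary safety reporting.

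**What to change.** In SAP 4.6.4.2, add one frequency or shift table, by cohort and total, from baseline to worst on-treatment dipstick category, for glucose, protein/albumin and haemoglobin/blood. Show n and % of children with a new or worse result, among those with a baseline and an on-treatment value, as SAP 4.6.3.2 does for blood tests. Use the SAP 3.3.1 baseline rule, state whether the end-of-treatment visit counts as on treatment, and keep the listing.

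The cost is one table plus a mapping of local-laboratory results to ordered categories (for example negative, trace, positive), fixed before database lock. Laboratory outputs are planned at all three data cut-offs, so no extra data collection is needed.

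If the sponsor prefers a listing only, the minimum is to declare and justify that in SAP Section 2 and reconcile it with protocol 8.4.5 and the SAP 4.2 endpoint table. That removes the inconsistency but leaves the component without a count.

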4.6.5 Other Laboratory Evaluations

4.6.5.1 Definitions and Derivations

Not applicable.

4.6.5.2 Presentations

Not applicable.

4.6.6 Vital Signs

4.6.6.1 Definitions and Derivations

Vital signs will be assessed at the timelines specified in the CSP.

The rules described in Sections 3.3.1, 3.3.4, and 3.3.5 of this document considering the definition of baseline, visit windows, and how to handle multiple records are followed.

4.6.6.2 Presentation

All vital signs (temperature, systolic and diastolic blood pressure, pulse rate, respiratory rate, and oxygen saturation) and growth parameters (height, weight, and BSA) will be summarised using descriptive statistics over time in terms of absolute values and change from baseline by scheduled visit.

Vital sign data will be presented graphically using boxplots for absolute values and changes from baseline by scheduled visit.

Individual BSA will be plotted against the study day. Historical measurements of weight and height will be presented on the x-axis as negative study days. Off-treatment data for participants who entered the long-term safety follow-up (participants < 5 years of age after 25 cycles of treatment or when they terminate treatment with selumetinib) will be included in the figure but presented with different symbols.

All vital sign, including BSA group, data will be listed.

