# 8.3.2 Height and Weight

Height and weight will be measured at the times outlined in the SoA. The participant's height will be recorded in cm and weight will be recorded in kg. Height and weight measurements will be performed in light clothing and with shoes off. Children under 2 years of age and those who are unable to stand stably enough to be measured in the standing position should be measured in the supine position on a measuring board (eg, Kiddimeter).

Collect all available documented previous height and weight measurements and growth curves if available at screening.

Height: The participants should take off shoes and socks, and heels should be placed against a wall

CONFIDENTIAL AND PROPRIETARY

Clinical Study Protocol -5.0 Selumetinib - D1346C00004 with ankles together. Height should be measured in a standing position with a stadiometer. Height measurements should be taken at approximately the same time of day for each visit, when possible. The height should be plotted on a standardised growth chart. In participants with known leg length discrepancy due to limb hypertrophy, height should be measured with the participant bearing weight on the limb without hypertrophy.

Body Surface Area should be calculated using the formula derived by Mosteller:

 $\sqrt{\text{(weight (kg) x height (cm) / 3600)}}$ 

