# 8.3.7 Knee/Wrist MRI/X-ray

Yearly growth assessments require integration of information including height measurements and bone age if clinically indicated, which should be plotted onto growth charts. Children with impaired growth velocity should be referred to a paediatric endocrinologist as clinically indicated for evaluation, and should be followed until they reach final adult height.

An MRI/X-ray of the knee will be performed at screening as specified in Table 2 and Table 3, and if clinically indicated, to monitor growth plates for any signs of physeal dysplasia. The imaging modality that is used at baseline (MRI/X-ray) must be used at all follow-up visits throughout the study. A wrist MRI/X-ray is acceptable if it is not possible to perform knee MRI/X-ray. The joint imaged (left/right, wrist/knee) must be consistent throughout the study, except occasions where MRI/X-ray of the joint imaged at baseline is not possible. Where feasible the knee/wrist MRI/X-ray will be performed at the same time as the PN volumetric MRI.

The investigator should regularly look for signs of physeal dysplasia (eg, joint pain and fatigue after exercising, abnormal gait, and spine irregularities). Children who show signs of physeal dysplasia at the time of selumetinib discontinuation should have a follow-up assessment after 30 days to evaluate the potential for reversibility.

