### Appendix F Blood Pressure

Blood pressure  $\leq$  the 95th percentile for age, height, and gender is required for enrolment. Because measurement accuracy is dependent on the use of proper BP cuff size, BP cuff should be selected as follows:

- Infant 8 to 11 cm.
- Child 12 to 16 cm.
- Small adult 17 to 22 cm.
- Adult 23 to 33 cm.

Table F19	Blood Pressure Levels for Children by Age and Height Percentile - Blood
	Pressure for Boys

Age	BP	Systolic BP (mmHg) Percentile of height					Diastolic BP (mmHg)								
years	percentile						Percentile of height								
		5 th	10 th	25 th	50 th	75 th	90 th	95 th	5 th	10 th	25 th	50 th	75 th	90 th	95 th
1	95 th	98	99	101	103	104	106	106	54	54	55	56	57	58	58
2	95 th	101	102	104	106	108	109	110	59	59	60	61	62	63	63
3	95 th	104	105	107	109	110	112	113	63	63	64	65	66	67	67
4	95 th	106	107	109	111	112	114	115	66	67	68	69	70	71	71
5	95 th	108	109	110	112	114	115	116	69	70	71	72	73	74	74
6	95 th	109	110	112	114	115	117	117	72	72	73	74	75	76	76
7	95 th	110	111	113	115	117	118	119	74	74	75	76	77	78	78
8	95 th	111	112	114	116	118	119	120	75	76	77	78	79	79	80
9	95 th	113	114	116	118	119	121	121	76	77	78	79	80	81	81
10	95 th	115	116	117	119	121	122	123	77	78	79	80	81	81	82
11	95 th	117	118	119	121	123	124	125	78	78	79	80	81	82	82
12	95 th	119	120	122	123	125	127	127	78	79	80	81	82	82	83
13	95 th	121	122	124	126	128	129	130	79	79	80	81	82	83	83
14	95 th	124	125	127	128	130	132	132	80	80	81	82	83	84	84
15	95 th	126	127	129	131	133	134	135	81	81	82	83	84	85	85
16	95 th	129	130	132	134	135	137	137	82	83	83	84	85	86	87
≥17	95 th	131	132	134	136	138	139	140	84	85	86	87	87	88	89

BP, blood pressure.

Source: National High Blood Pressure Education Program Working Group on High Blood Pressure in Children and Adolescents 2004.

Age	BP		Systolic BP (mmHg) Percentile of height					Diastolic BP (mmHg)							
years	percentile									Perce	ntile of	f heigh	t		
		5 th	10 th	25 th	50 th	75 th	90 th	95 th	5 th	10 th	25 th	50 th	75 th	90 th	95 th

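### SAP 4.6.6.2 analyses height, weight, BSA and blood pressure only on raw scales, so expected growth is mixed with any drug effect, chiefly at DCO2 and DCO3

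*SAP*

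**What the plan says.** SAP 4.6.6.2 places two groups of variables in one summary. The first is "All vital signs (temperature, systolic and diastolic blood pressure, pulse rate, respiratory rate, and oxygen saturation". The second is "growth parameters (height, weight, and BSA) will be summarised using descriptive statistics over time in terms of absolute values and change from baseline". Results are given at each planned visit. SAP 3.3.1 makes change a plain difference: "the change from baseline variables will be calculated as the posttreatment value" minus the baseline value. Boxplots are planned for vital signs, and all data are listed.

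The only individual growth display is of BSA: "Individual BSA will be plotted against the study day". For the pre-treatment period the SAP adds that "Historical measurements of weight and height will be presented on the x-axis as negative study days". No on-treatment height trajectory is plotted for any child.

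The protocol uses age and sex references, but only at site level and at entry. Section 8.3.2 says "The height should be plotted on a standardised growth chart" and asks sites to collect earlier heights, weights and growth curves. Section 8.3.7 says "Children with impaired growth velocity should be referred to a paediatric endocrinologist as clinically indicated for evaluation". Appendix F sets an upper limit on blood pressure at entry: "the 95th percentile for age, height, and gender is required for enrolment". None of these references is carried into a SAP derivation.

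**The concern.** Growth is a named safety question here. Protocol Table 4 lists physeal dysplasia as a potential risk that could lead to limb shortening. Its reassurance from earlier experience rests on longitudinal height and growth velocity in treated children. Protocol 4.1.2 and SAP 4.6.2.1 explain that the long-term follow-up exists because long-term safety data are lacking for children who start below age 3. That is also when growth is fast and raw change is hardest to read.

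With no control arm, a table of mean height or weight change by visit will rise in a study where the drug slows growth and in one where it does not. A reader of the study report could not tell the two apart without applying an outside reference to the listings.

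**Working it through.** **Does the SAP contain any referenced measure?** The SAP was read for an SD score, growth centile, growth velocity or blood pressure centile applied to height, weight, BSA or blood pressure. There is none. Laboratory values, by contrast, are compared with reference ranges and graded (SAP 4.6.3).

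**Time for growth to accumulate.**
- Full treatment: 25 cycles × 28 days = 700 days; 700 / 365.25 = 1.92 years.
- Minimum follow-up at DCO1: 3 × 28 = 84 days; 84 / 365.25 = 0.23 years.
- DCO3: a child who starts at age 1 can be followed to age 5.

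**What the BSA plot can show.** Protocol 8.3.2 gives BSA = √(weight × height / 3600).
- Height 5% low with weight unaffected: √0.95 = 0.975, so BSA falls by only 2.5%.
- Height 5% low with weight 5.3% high: 0.95 × 1.053 = 1.00, so BSA does not change.

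**How far a reference moves with age alone.** The documents give no reference values for height, weight or BSA, so no figure is computed for them. They do give the 95th-percentile blood pressure limit (Appendix F, Tables F19 and F20). At the 50th height percentile, in mmHg:

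| Age | Boys systolic | Boys diastolic | Girls systolic | Girls diastolic |
|---|---|---|---|---|
| 1 to 3 | 103 to 109 (+6) | 56 to 65 (+9) | 104 to 107 (+3) | 58 to 67 (+9) |
| 2 to 4 | 106 to 111 (+5) | 61 to 69 (+8) | 105 to 108 (+3) | 63 to 70 (+7) |
| 5 to 7 | 112 to 115 (+3) | 72 to 76 (+4) | 110 to 113 (+3) | 72 to 75 (+3) |

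Over all starting ages from 1 to 6, the two-year shift at this height percentile is +2 to +6 systolic and +2 to +9 diastolic. From age 1 to 5 the diastolic limit rises by 16 in boys (56 to 72) and 14 in girls (58 to 72).

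At the DCO1 minimum the largest shift is about 1 mmHg: for a boy aged 1 to 2 the diastolic limit goes from 56 to 61, and 5 mmHg per year × 0.23 years = 1.15 mmHg.

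**The case against.** The case for the plan has real substance.

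- **Other analyses address growth-plate risk.** Knee or wrist imaging is a named primary safety variable, tabulated by visit (SAP 4.6.10.2). Physeal dysplasia is an AESI that includes short stature (SAP Table 16). Sites chart growth. This stands, so it would be wrong to infer that the plan is blind to growth-plate toxicity. Still, imaging does not measure linear growth, and an AESI count depends on what investigators report.
- **The raw summaries are not crude pooling.** Absolute values are tabulated as well as change, and SAP section 4 shows the 4 to under 7 and 1 to under 4 cohorts separately. This stands in part: each Global Cohort still spans three years of age, and the Japan Cohort spans 1 to under 7.
- **BSA masking is limited to the plot.** Height and weight are also summarised separately, so a reader should not infer that a height deficit is hidden from the whole analysis. The SAP amendment history gives a reason for plotting BSA: it was judged more meaningful than weight or height.
- **The primary safety analysis is little affected.** A reader might infer that it is compromised. It is DCO1, where drift at minimum follow-up is small, and the primary safety endpoint names weight and vital signs but not height or BSA.
- **Blood pressure is a weaker case.** It is neither a Table 4 risk nor an AESI. The Appendix F figures are shifts in an upper entry limit, not expected mean changes, so they do not show that a raw rise of that size carries no drug signal.
- **Within-child history is used.** Historical measurements appear on the BSA plot. That is a limited comparison: it is not summarised and does not show height as its own trajectory.

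**Conclusion.** The point holds as a gap in the descriptive safety analysis. Height, weight, BSA and blood pressure are presented only on raw scales, without any age and sex reference or growth velocity, and the one individual growth plot can mask a height shortfall. Expected growth is therefore mixed with any drug effect. This matters chiefly at DCO2 and DCO3 and little at DCO1.

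The size can be shown only indirectly. A 5% height deficit appears as 2.5% in BSA, or not at all if weight is 5.3% high. The protocol's diastolic limit moves by 2 to 9 mmHg in two years at the median height centile. The second figure assumes that the movement of an upper limit illustrates drift with age; it does not estimate mean change. The effect on height and weight tables cannot be sized from the documents.

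The stronger reading, that the plan cannot address growth safety at all, is not supported, because imaging and AESI analyses are planned. Nor would standardising fully isolate a drug effect: without a control arm, disease effects on growth remain.

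**What to change.** In SAP 4.6.6.2, for DCO2 and DCO3:

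- Derive height-for-age and weight-for-age SD scores by sex from one named growth reference. Use age on the measurement date, since SAP 4.1.4.1 otherwise makes age at screening the analysis age.
- State how the change from supine to standing measurement is handled. Protocol 8.3.2 measures children under 2, and those who cannot stand stably, supine.
- Summarise change from baseline in SD score by visit and cohort, plus annualised height velocity.
- Plot individual height SD score against study day, including historical heights where available.
- Keep the raw tables as support.

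As an optional supplement, report by visit the number and percentage above the Appendix F 95th percentile for blood pressure, using the same growth reference to obtain height percentile, because Appendix F gives no heights.

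The cost is SAP wording and programming. Date of birth, sex, height, weight and blood pressure are already collected, and no sample size or power figure changes. There are two downsides: one reference must serve a multinational sample, and historical heights will be incomplete.
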